12 PUBLICATION PLAN19

13 REFERENCES20

14 ATTACHMENTS20

List of Abbreviations

List all abbreviations used in protocol

AE	Adverse Event
CFR	Code of Federal Regulations
CRF	Case Report Form
DSMB	Data and Safety Monitoring Board
DSMP	Data and Safety Monitoring Plan
FDA	Food and Drug Administration
GCP	Good Clinical Practice
HIPAA	Health Insurance Portability and Accountability Act of 1996
ICH	International Conference on Harmonisation
IDS	Investigational Drug Services
IRB	Institutional Review Board
PHI	Protected Health Information
SAE	Serious Adverse Event

CONFIDENTIAL

This material is the property of the University of Minnesota. Do not disclose or use except as authorized in writing by the study sponsor

Study Summary

Title	A randomized double blinded study to examine the use of N-acetyl cysteine for the prevention and treatment of HAAF in patients with type 1 diabetes
Short Title	NAC for HAAF
Protocol Number	NA
Phase	I/II
Methodology	This is a single center, double blind randomized cross over design trial that will compare the impact of N-acetyl cysteine (200 mg/kg) vs. saline infusion during experimental hypoglycemia on day one on the responses to experimental hypoglycemia on day two. 18 participants will be studied twice, 8 weeks apart. On each occasion they will undergo a 2 hour hypoglycemic clamp (target 50 mg/dl) in the morning and in the afternoon on day one and then again on the morning of day 2. During the morning clamps, samples will be collected for later measurement of serum epinephrine levels, plasma and red blood cell NAC, cysteine, and glutathione concentrations and GSH/GSSG ratios (redox status), and participants will be asked to complete a hypoglycemia symptom questionnaire
Study Duration	10-12 weeks per subject
Study Center(s)	Single Center
Objectives	Primary endpoint will be the within person difference in epinephrine secretion during the morning episodes of hypoglycemia on days one and two under the two treatment conditions. Epinephrine secretion during hypoglycemia is assessed by collecting blood samples for measurement of epinephrine concentrations at baseline and every 15 minutes during the period of hypoglycemia (starting at point where blood glucose is first \leq 55 mg/dl) in the clamp studies done in the mornings of days 1, 2, and 3 of both parts 1 and 2.
Number of Subjects	36
Diagnosis and Main Inclusion Criteria	Healthy adults ages 18-65 years with hemoglobin A1c < 6.0%. Exclusion criteria will include history of diabetes, hyperglycemia, stroke, seizures, arrhythmias, active cardiac disease; pregnancy or plan to become pregnant during the study period; diagnosis of asthma; use of anti-oxidants or drugs that can alter glucose metabolism; and concomitant medical problems that may prevent the subject from successfully completing the protocol.
Study Product, Dose, Route, Regimen	N-acetyl cysteine 200 mg/kg (or saline) IV infusion (given as a 150 mg/kg loading dose over the first hour and then followed by a 50 mg/kg maintenance dose infused over the next 4 hours on day 1 of each of the two parts of the study)
Duration of administration	5 hours on day one

Reference therapy	NAC will be tested against placebo.
Statistical Methodology	
Our primary outcome is the peak epinephrine response during the third hypoglycemic clamp of each infusion experiment, thus each participant will have two observations: one from their NAC infusion experiment and one from their saline infusion experiment. We will fit a general linear mixed model with fixed effects for treatment (NAC vs. saline), treatment order (NAC first vs. saline first), and period (Part 1 vs. Part 2) and a random effect for participant. We will also consider adjustment for important baseline characteristics, such as age, gender, and duration of diabetes. Diagnostics will be examined to assess model assumptions. Secondary outcomes include: the within-person difference in peak epinephrine response between the first hypoglycemic clamp (when an infusion is given) and the third hypoglycemic clamp (when no infusion is given) of each infusion experiment; symptom scores during the third hypoglycemic clamp of each infusion experiment; and the within-person difference in symptom scores between the first hypoglycemic clamp and the third hypoglycemic clamp of each infusion experiment

CONFIDENTIAL

1 Introduction

This document is a protocol for a human research study. This study will be conducted according to US and international standards of Good Clinical Practice (FDA Title 21 part 312 or 812 and International Conference on Harmonisation guidelines), applicable government regulations and Institutional research policies and procedures.

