2.1 General Design

This is a single center, double blind randomized cross over design trial that will compare the impact of NAC vs. saline infusion during experimental hypoglycemia on day one on the responses to experimental hypoglycemia on day two. Figure 1 shows the protocol in schematic form. We intend to enroll 18 individuals to obtain the complete data sets from 15 participants.

Expected duration of subject participation is 10-12 weeks. This study will consist of a screening visit and two 2-day intervention visits separated by approximately 8 weeks.

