4.8.4 Return or Destruction of Study Drug

At the completion of the study, there will be a final reconciliation of drug shipped, drug consumed, and drug remaining. This reconciliation will be logged on the drug reconciliation form, signed and dated. Any discrepancies noted will be investigated, resolved, and documented prior to return or destruction of unused study drug. Drug destroyed on site will be documented in the study files.

5 Study Procedures

This study will consist of a screening visit and two 3-day intervention visits separated by approximately 8 weeks.

At the screening visit (approximately 2-4 days prior to study day one) informed consent will be obtained, the clinical history will be reviewed to be certain a volunteer meets the inclusion criteria and baseline hemoglobin A1c will be obtained.

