6.1 Sample Size Determination

We propose a two-period two-treatment cross-over study, where each participant gets NAC infusion and saline infusion, in randomized order as shown in Figure under 2.1. Our primary outcome is the peak epinephrine response during the third hypoglycemic clamp of each infusion experiment, thus each participant will have two observations: one epinephrine response from their NAC infusion experiment and one epinephrine response from their saline infusion experiment. We expect to recruit 18 individuals in order to complete 15 studies. Additional participants will be recruited if needed to have 15 completed studies. If NAC prevents HAAF, then the epinephrine response during the third hypoglycemic clamp after NAC infusion will still be high, while the epinephrine response during the third hypoglycemic clamp after saline infusion will be blunted. Therefore ***this within-person difference in epinephrine response will be large and positive***. Assuming a one-sided type I error of 5% and a power of 85%, we can detect an epinephrine response difference between NAC and saline of at least 154 units. This magnitude of difference is comparable to the difference between healthy controls and subjects with T1DM and hypoglycemia unawareness that we found in a previous study. In that study, participants underwent a hyperinsulinemic hypoglycemic clamp and the epinephrine response during hypoglycemia in the subjects with T1DM was 121 ± 168 pg/ml vs. 278 ± 134 pg/ml in controls.

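### The synopsis gives 36 subjects, but its own Methodology row, Sections 2.1 and 6.1 and the stopping table all run to 18, and nothing explains 36

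*Combined protocol and SAP*

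**What the plan says.** The Study Summary gives two sizes. Its row "Number of Subjects" holds the value 36. Its Methodology row says "18 participants will be studied twice, 8 weeks apart". The Study Summary does not mention 15 completers.

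The body of the plan is consistent. Section 2.1: "We intend to enroll 18 individuals to obtain the complete data sets from 15 participants". Section 6.1: "We expect to recruit 18 individuals in order to complete 15 studies", followed by "Additional participants will be recruited if needed to have 15 completed studies". No upper limit on recruitment is given. The design in Section 6.1 is a cross-over: "We propose a two-period two-treatment cross-over study, where each participant gets NAC infusion and saline infusion". The stopping table in Section 7.5 gives boundaries for 1 to 18 participants who have completed at least the Part 1 infusion, and nothing beyond.

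A separate inconsistency concerns the schedule. The Objectives row of the Study Summary samples epinephrine "in the clamp studies done in the mornings of days 1, 2, and 3 of both parts 1 and 2", and Section 5 opens with "two 3-day intervention visits separated by approximately 8 weeks". Section 2.1 has two-day visits, Section 2.2 samples on days 1 and 2, and the visit table in Section 5 lists only Days 1 and 2 in each part.

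**The concern.** The synopsis is where an ethics board, a monitor or a safety board looks first for the number of people to be exposed. Here it gives two numbers that differ by a factor of two. Each participant has three clamps per part, so six in all, plus one NAC infusion. For 18 people that is 18 × 6 = 108 hypoglycemic clamps; for 36 it is 36 × 6 = 216. If 36 were the intended size, the power statement would not describe the trial, and participants 19 to 36 would have no allergy boundary.

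**Working it through.** **Inputs.** From Section 6.1: one-sided type I error 5%, power 85%, detectable difference 154 units, 15 completers from 18 recruited, SDs of 168 and 134 pg/ml from an earlier study. Not given: the SD of the within-person difference. I assume zero correlation between the two quoted SDs and then vary it.

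**Enrolment.** The implied non-completion is 3/18 = 16.7%, and 15 / (1 − 3/18) = 18. The step from 15 to 18 is correct.

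**SD of the difference.** √(168² + 134²) = √46,180 = 214.9.

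**The plan's own figure, n = 15.** By normal approximation the detectable difference is (1.645 + 1.036) × 214.9 / √15 = 148.8. By noncentral t on 14 df it is 156.6. The two bracket 154. In reverse, (2.681 × 214.9 / 154)² = 14.0 completers by normal approximation, or 16 by noncentral t. Power at 154 with 15 completers is 84.0% (t) or 87.1% (normal). Section 6.1 is therefore broadly reproduced.

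**If 36 were the size.** At the same completion rate, 36 enrolled gives 36 × 15/18 = 30 completers.

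**Varying the correlation.** SD = √(168² + 134² − 2ρ × 168 × 134); one-sided paired t on n − 1 df. Entries are the detectable difference at 85% power, with power at 154 units in brackets.

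| ρ | SD of difference | n = 15 | n = 30 | n = 36 |
|---|---|---|---|---|
| 0 | 214.9 | 156.6 (84.0%) | 107.7 (98.6%) | 97.9 (99.5%) |
| 0.25 | 186.9 | 136.1 (91.7%) | 93.7 (99.7%) | 85.2 (99.9%) |
| 0.5 | 153.8 | 112.1 (97.9%) | 77.1 (>99.9%) | 70.1 (>99.9%) |

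Positive correlation also takes n = 15 below 154, so the close match at 15 depends on ρ near zero. It takes 30 and 36 further away still. Only a correlation near −1 would bring 30 completers close to 154: at ρ = −1 the SD is 168 + 134 = 302 and the detectable difference 151.4. With 36 completers it would still be only 137.6.

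**Stopping table against the replacement rule.** The table counts people who have completed the Part 1 infusion and ends at 18. Recruitment continues until 15 complete. If four people finish the Part 1 infusion but not the study, 15 + 4 = 19 have passed Part 1, and the table has no entry for them. This gap remains whatever the synopsis row says.

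**The case against.** The strongest reply is that one cell of a summary table is out of line while the design section, sample-size section and stopping table agree. That stands: Section 6.1 is not in error. A reader might infer that the trial is mis-sized by a factor of two, or that 216 clamps will be performed. The documents do not support either reading; both require following the one row that the rest of the plan contradicts.

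A second reply is that 36 may have a meaning. It equals 18 participants × 2 infusion experiments, or it could be a recruitment ceiling or a holdover. It also matches a parallel-group count: 15 per arm gives a detectable difference of 152.5 by two-sample t, and 30 completers would need 36 enrolled at the same completion rate. None of these is stated, and Section 6.1 describes a cross-over with both observations from each person. So the origin of 36 is unknown and the sponsor should say what it counts. If it counts experiments, the row label is wrong.

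A third reply is that the power figures rest on an SD that the plan does not give, built from between-person SDs in two different groups. That also stands. The figures show which size Section 6.1 was built on; the contradiction between 36 and 18 does not need them.

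Finally, 18 is an expected number and not a cap, so correcting the row alone leaves the maximum undefined.

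**Conclusion.** The contradiction is real and confined to the row "Number of Subjects": 36 there, against 18 in the Methodology row, Sections 2.1 and 6.1 and the end of the stopping table. The 15 completers appear only in Sections 2.1 and 6.1. Under the cross-over described, with an assumed SD of the difference of 214.9, the power statement fits about 15 completers and not 30 to 36; zero or positive correlation leaves that conclusion unchanged. The planned analysis is unaffected if 18 and 15 stand. The row should still be corrected, because it misstates a figure on which approval and safety oversight rely. The missing recruitment maximum comes from the replacement rule and needs its own sentence. The schedule wording is a separate inconsistency and adds nothing to the sample-size point.

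**What to change.** 1. Change the synopsis row to 18 enrolled for 15 completers, the figures that Section 6.1 justifies.
2. If 36 is meant as a recruitment maximum or as a count of infusion experiments, say so and label it accordingly. If 36 participants are truly intended, redo Section 6.1.
3. State in Section 6.1 the maximum number who may be enrolled, replacements included. If it exceeds 18, extend the stopping table in Section 7.5 to that number.
4. Separately, reconcile the day-3 sampling in the Objectives row and the three-day visits at the start of Section 5 with the two-day schedule in Section 2.1 and the visit table.

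If 18 stands, items 1 and 4 are wording changes with no added participants or procedures. Item 3 costs one sentence and, if the maximum exceeds 18, a recalculation of the boundary.

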1.1 Background

The purpose of this project is to evaluate N-acetyl cysteine (NAC) as a therapy for the prevention and treatment of hypoglycemia associated autonomic failure (HAAF) in patients with type 1 diabetes. Impaired awareness of hypoglycemia occurs in approximately 25% of adults with type 1 diabetes and is associated with a six fold higher risk of having severe hypoglycemia that requires the assistance of another to recognize and treat. HAAF is also the primary barrier to achieving the level of glucose control necessary to prevent the microvascular complications of the disease and contributes to the mortality seen in patients with T1DM. To fully evaluate NAC as a therapy, it is imperative that its action in humans be examined.

1.2 Investigational Agent

N-acetyl cysteine (or saline) IV infusion given as a 150 mg/kg loading dose over the first hour and then follow that with a 50 mg/kg maintenance dose infused over the next 4 hours

1.3 Preclinical Data

In animal models, administration of N-acetyl cysteine (NAC) during episodes of hypoglycemia prevents the development of HAAF, possibly by preventing the hypoglycemia induced rise in hypothalamic reactive oxygen species known to occur during acute episodes of hypoglycemia .

1.4 Clinical Data to Date

The sponsor investigator completed a randomized placebo controlled trial of naltrexone as a therapy of patients with type 1 diabetes hypoglycemia unawareness in which 30 subjects enrolled over 3 years. One third were unable to complete the study: one because of rising liver function tests during the drug treatment and the rest for technical reasons related to the magnetic resonance imaging part of the study. In another study in which the default mode network was evaluated during hypoglycemia, we enrolled 11 people with type 1 diabetes and awareness of hypoglycemia, 9 people with type 1 diabetes and unawareness' of hypoglycemia, and 11 controls over an 18 months period. NAC has not been used in humans as a treatment of hypoglycemia unawareness in type 1 diabetes.

CONFIDENTIAL

1.5 Dose Rationale and Risk/Benefits

This is a proof of principle experiment in which the maximal dose of NAC approved for human use will be intravenously infused to ensure that high serum concentrations of the drug are achieved. We propose a 200 mg/kg dose in which we will infuse a 150 mg/kg loading dose over the first hour followed by a 50 mg/kg maintenance dose infused over the next 4 hours, as is recommended for acetaminophen overdose,

In the package insert, the manufacturer includes a table that lists the incidence of drug related adverse events following drug administration. Data from 180 individuals are included in the table; 10 experienced mild anaphylactoid reactions (6%), 16 experienced moderate reactions (9%) and 2 experienced severe reactions (1%). All of these reactions occurred within the first 2 hours following the drug administration, following a dosage schedule we plan to use for this protocol. The package insert also includes a table that summarizes the adverse events observed in 76 published articles in which NAC was intravenously infused. The Rocky Mountain Poison and Drug Center prepared this table from information collected on 2040 subjects. 1.67% were noted to have urticaria, 1.47% had vasodilatation and rash, 0.78% had hypotension. Our protocol excludes individuals with asthma or with a history of bronchospasm in an effort to reduce the risk of severe anaphylactoid reactions. We believe the small risk of adverse events from NAC exposure are reasonable given the impact of hypoglycemia unawareness on patients with diabetes. The first sign that these patients have hypoglycemia is confusion or loss of consciousness, both of which can lead to injury from accidents. If untreated, this hypoglycemia could cause seizures and death. The number of patients with type 1 diabetes who experience hypoglycemia unawareness has been estimated to be as high as 25%.

Primary Objective

Primary endpoint will be the within person difference in epinephrine secretion during the morning episodes of hypoglycemia on days one and two under the two treatment conditions. Epinephrine secretion during hypoglycemia is assessed by collecting blood samples for measurement of epinephrine concentrations at baseline and every 15 minutes during the period of hypoglycemia (starting at point where blood glucose is first ≤ 55 mg/dl) in the clamp studies done in the mornings of days 1 and 2 of both parts 1 and 2.

Secondary Objective

Secondary endpoint will be within person difference in symptom scores collected during the morning episodes of hypoglycemia on days one and two under the two treatment conditions. Symptom scores during hypoglycemia will be quantified using a previously validated questionnaire at baseline and at the end of the hypoglycemic clamp studies done in the mornings of days 1 and 2 of both parts 1 and 2..

CONFIDENTIAL

2 Study Design

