3.1 Inclusion Criteria

- Healthy volunteer
- Age 18 – 65 years
- Hemoglobin A1c < 6.0%

CONFIDENTIAL

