3.2 Exclusion Criteria

- History of diabetes, hyperglycemia, stroke, seizures, arrhythmias, active cardiac disease
- Pregnancy or plan to become pregnant during the study period
- Diagnosis of asthma (increases risk of hypersensitivity reactions to NAC)
- Use of anti-oxidants or drugs that can alter glucose metabolism
- Concomitant medical problems that may prevent the subject from successfully completing the protocol
- Unwillingness to avoid exercise during the 7 days before each part of the study

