3.3 Subject Recruitment and Screening

Subjects will be recruited from a registry of normal volunteers who are interested in participating in research that is maintained by the investigator. In addition, subjects will be drawn from the community using IRB approved public notices. The only laboratory testing necessary to meet inclusion/exclusion criteria will be a hemoglobin A1c done in the last month.

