6.3 Subject Population(s) for Analysis

In this version of the protocol, we intend to only study healthy volunteers. In the original version, we intended to enroll humans with type 1 diabetes of less than 20 years duration, with A1c 6.9-8.2%, who were aware of hypoglycemia but were unable to reach our recruitment goals with this population. More than 45 potential participants were contacted over 14 months and only one subject was able to complete the entire protocol. The reasons potential participants refused enrollment included strong preferences to not experience hypoglycemia and inability to commit the time necessary to complete the study. Previously our group has had no trouble enrolling enough normal volunteers to participate in studies in which they were asked to experience several periods of hypoglycemia. Thus, we believe that we will meet our recruitment goals by changing the population to normal volunteers. In addition, this is a proof of principle study in which the impact of NAC on hypoglycemia induced blunting of the counterregulatory response will be measured. Normal volunteers who participate in this protocol are expected to have the same degree of hypoglycemia induced blunting in their counterregulatory response as patients with type 1 diabetes and normal awareness of hypoglycemia. Therefore, this redesign will allow us to determine if NAC works under controlled conditions. If it does, it will provide rationale to use in in patient populations in the future.

Exclusion criteria will include history of diabetes, hyperglycemia, stroke, seizures, arrhythmias, active cardiac disease, pregnancy or plan to become pregnant during the study period; diagnosis of asthma (increases risk of hypersensitivity reactions to NAC); use of anti-oxidants or drugs that can alter glucose metabolism; concomitant medical problems that may prevent the subject from successfully completing the protocol; and an unwillingness to avoid exercise during the 7 days before each part of the study.

7 Safety and Adverse Events

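### Section 1.5 says a history of bronchospasm is excluded to limit severe NAC reactions, but no exclusion list contains that criterion

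*Combined protocol and SAP*

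**What the plan says.** Section 1.5 reports anaphylactoid reactions to NAC from the package insert and then gives the mitigation: "Our protocol excludes individuals with asthma or with a history of bronchospasm in an effort to reduce the risk of severe anaphylactoid reactions". That describes two exclusions, asthma and a history of bronchospasm.

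The criteria lists contain one of them:

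- Section 3.2 lists "Diagnosis of asthma (increases risk of hypersensitivity reactions to NAC", with the reason given in parentheses. It also has a general item: "Concomitant medical problems that may prevent the subject from successfully completing the protocol".
- Section 6.3 restates the list and has "diagnosis of asthma (increases risk of hypersensitivity reactions to NAC".
- The Study Summary gives a shortened list: "diagnosis of asthma; use of anti-oxidants or drugs that can alter glucose metabolism".

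On the inclusion side, Section 3.1 asks for a "Healthy volunteer" without defining the term. For screening, Section 5 says "the clinical history will be reviewed to be certain a volunteer meets the inclusion criteria", and Section 3.3 adds: "The only laboratory testing necessary to meet inclusion/exclusion criteria will be a hemoglobin A1c done in the last month". The only other mention of bronchospasm is in Section 7.1, where its intensive emergency treatment is an example of a serious adverse event.

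**The concern.** The exclusion is the only measure Section 1.5 names for lowering the risk of severe reactions. Half of it is missing from the criteria that decide who is enrolled. A reader of Section 1.5, such as an IRB member, would credit the trial with a protection that Section 3.2 does not provide.

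This matters more than usual for two reasons. The participants are now healthy volunteers, while Section 1.5 still justifies the risk by the burden of hypoglycemia unawareness in people with diabetes. NAC is also given at what Section 1.5 calls the maximal approved dose, and in a crossover nobody who finishes avoids it: assignment to saline first only postpones exposure to Part 2.

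There is a smaller consequence for withdrawal. Section 3.4.1 withdraws anyone who comes to meet an exclusion criterion after enrolment. With bronchospasm absent from the list, an episode between the two Parts does not clearly trigger withdrawal.

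**Working it through.** This is a check of text against text; the plan has no figure to reproduce.

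**Step 1. Compare the statements.**

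| Place | Asthma | History of bronchospasm |
|---|---|---|
| 1.5 (rationale) | yes | yes |
| 3.2 (operative list) | yes | no |
| 6.3 (restatement) | yes | no |
| Study Summary (shortened) | yes | no |

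None of the three lists carries the bronchospasm criterion. The Study Summary is abbreviated, so its silence counts for less than that of 3.2 and 6.3.

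**Step 2. Ask whether another criterion covers it.** Take a volunteer with one past episode of bronchospasm, now resolved, and no asthma diagnosis.

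- Asthma item: not met, since there is no such diagnosis.
- General item in 3.2: it concerns concomitant problems that may stop the person completing the protocol. A resolved episode need not be concomitant, and need not prevent completion.
- Healthy volunteer in 3.1: an investigator could use it to turn the person away, but nothing requires this.
- Screening: a history review plus hemoglobin A1c. The protocol text specifies no question about bronchospasm.

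Read literally, the criteria admit this person.

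**Step 3. Ask whether later safeguards make up for it.** Section 5 gives diphenhydramine before the infusion. Section 2.4 schedules allergy-symptom questions, including shortness of breath, at baseline and 30, 60 and 90 minutes. Section 7.5 stops the infusion for symptoms such as trouble breathing and sets a DSMB boundary. These reduce, detect or limit a reaction. None keeps a person with this history from receiving NAC.

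**Step 4. Background risk quoted in 1.5.** Reactions among 180 people: 10 mild, 16 moderate and 2 severe. The total is 10 + 16 + 2 = 28, and 28/180 = 15.6%; severe alone is 2/180 = 1.1%. These figures are not broken down by history of bronchospasm, so they do not give the added risk in such a person.

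**Step 5. Rough size.** The planned enrolment is 18 (Sections 2.1 and 6.1; the separate line in the Study Summary giving 36 is not used here). The prevalence *p* of past non-asthmatic bronchospasm among volunteers is not in the documents; the range 1% to 5% is assumed for illustration.

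- Expected number = 18 × *p*: 18 × 0.01 = 0.18; 18 × 0.05 = 0.90.
- Chance of at least one = 1 − (1 − *p*)^18: 1 − 0.99^18 = 0.165; 1 − 0.95^18 = 0.603.

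Both calculations suppose that no such volunteer is removed by investigator judgement, so for a given *p* they are upper limits.

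**The case against.** The strongest reply is that Section 1.5 is part of the same protocol and says these people are excluded, so infusing one would contradict the protocol itself. At a single center, an investigator who knows this can use the healthy-volunteer criterion, the history review and the general item in 3.2. That item can even be stretched: a reaction that stops the infusion means withdrawal, so a condition that raises that risk may prevent completion. The screening form is not among the documents and may ask about bronchospasm. This narrows the gap, but it relies on judgement and on staff reading the rationale as a criterion. It does not clearly reach a resolved past episode.

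The withdrawal point is open to more doubt. New bronchospasm would be an adverse event that Section 7.2 requires the investigator to ask about, and as a current problem it fits the general item better than a remote episode does. If it stopped a Part 1 infusion, 3.4.1 and 7.5 already withdraw the person. If Part 1 was NAC, Part 2 is saline, so no second NAC exposure follows. What remains is a saline-first participant with an episode between Parts: a narrow case, and only secondary support.

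The prevalence range is an assumption, as stated, and the conclusion does not depend on it.

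Finally, one could argue that 1.5 is the text in error, since 3.2 and 6.3 agree with each other. The documents do not settle which was intended. Deleting the phrase from 1.5 would restore consistency, but only by giving up a protection the rationale presents as already in force.

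**Conclusion.** The concern holds. Section 1.5 claims a safety exclusion that Sections 3.2 and 6.3 and the Study Summary do not contain, and no other criterion clearly supplies it. The mismatch rests on the current text alone and needs no assumption.

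Its practical size is small: probably under one person in 18, even at the assumed 5% prevalence. The excess risk of a severe reaction in that person is unknown from the documents. The change should be made because it concerns participant safety and is easy to make. Epinephrine as the primary endpoint, the sample size, the type I error and the mixed model are not touched.

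**What to change.** Add a history of bronchospasm to the exclusion criteria in Section 3.2, beside the asthma item, and repeat it in Section 6.3 and the Study Summary so that all three match Section 1.5. Make it an explicit question in the clinical history taken at screening. The withdrawal rule in 3.4.1 then covers it without rewording.

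The cost is one phrase in three places, one question in a history already being taken, and perhaps a rare extra screen failure.
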